4.5 SECONDARY ENDPOINTS

4.5.1 Infant B Cell Levels at 6 Weeks of Life

Infant B cell levels (CD19+ cells, absolute counts and percentage of lymphocytes) measured at Week 6 of life will be summarized descriptively in the FASI, irrespective of the occurrence of any ICEs identified for the primary endpoint.

4.5.2 Infant Serum Concentration of Ocrelizumab

To evaluate whether there is placental transfer of ocrelizumab from the mother to the infant, serum ocrelizumab concentrations are measured in the umbilical cord blood at birth (within 1 hour after delivery) and at 6 weeks of life. Summary statistics for the serum concentration of ocrelizumab in the umbilical cord and in the infant at Week 6 will be presented (including breastfeed prior to sample taken) in the FASI, and a corresponding listing produced.

Correlation between maternal OCR concentration and OCR concentration in infant will be explored in order to characterize the exposure and transfer relationship.

Serum ocrelizumab concentration reported as below limit of quantification (BLQ) will be imputed to zero for the calculation of summary statistics.

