2. OBJECTIVES AND ENDPOINTS

This study will evaluate the potential placental transfer of ocrelizumab in women with CIS or MS (in line with the locally approved indications) whose last dose of ocrelizumab was administered anytime from 6 months before the LMP through to the first trimester of pregnancy (up to gestational Week 13), and the corresponding pharmacodynamic effects, particularly B-cell levels, in the infants.

Specific objectives and corresponding endpoints for the study are outlined below.

Table 1 Objectives and Corresponding Endpoints

Objectives	Corresponding Endpoints
Primary Outcome Measure	
• To evaluate whether infants potentially exposed to ocrelizumab during pregnancy present with postpartum B-cell depletion	 Proportion of infants with B-cell levels (CD19 + cells, absolute counts) below the LLN, measured at Week 6 of life

ASQ-3 = Ages and Stages Questionnaire, version 3; EDSS = Expanded Disability Status Scale; HBV = hepatitis B virus; Hib = Hemophilus influenzae type b; LLN = lower limit of normal; MMR = measles, mumps, and rubella; MS = multiple sclerosis; PCV-13 = 13-pneumococcal conjugate vaccine; SARS-CoV-2 = severe acute respiratory syndrome coronavirus 2; sNfl = serum neurofilament light chain; WHO = World Health Organization.

Table 1 Objectives and Corresponding Endpoints (cont.)

Objectives	Corresponding Endpoints	
Secondary Outcome Measures		
To evaluate B-cell levels in infants potentially exposed to ocrelizumab during pregnancy	 B-cell levels (CD19 + cells, absolute counts and percentage of lymphocytes) measured at Week 6 of life 	
• To evaluate whether there is placental transfer of ocrelizumab from the mother to the infant	• Serum concentration of ocrelizumab in the umbilical cord blood at birth (target time frame of blood sampling: within 1 hour after delivery)	
	 Serum concentration of ocrelizumab in the infant at Week 6 of life 	
To evaluate whether infants potentially exposed to ocrelizumab during pregnancy are able to mount humoral immune responses to clinically relevant vaccines	• Mean titers of antibody immune response(s) to common childhood vaccinations with full or partial doses given prior to 1 year, which include responses to diphtheria, tetanus, pertussis , Hib, PCV-13, MMR, and HBV	
	 Proportion of infants with positive humoral response (seroprotective titers; as defined for the individual vaccine) to vaccines 	

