3.1.3 Pregnancy and Early Postpartum Period

Mother:

- Pregnancy period: Laboratory and clinical assessments during the third trimester (gestational Week 35 [±14 days]) will be performed in accordance with planned prenatal care visits, whenever possible. To reduce the burden of visits on the mothers, results from physical and obstetric examinations, as well as neurological examinations, done as part of routine care may be used. *All* visit samples may be collected by home nurse visit. Women may be given vaccines (e.g., for *Bordetella pertussis*) as part of routine obstetric care (note: live or live-attenuated vaccines are not recommended during ocrelizumab treatment and until B-cells return to normal level). Ocrelizumab must not be administered after the woman is enrolled in the study and until the infant's birth. Should this happen, the woman will be discontinued from the study.
- Early postpartum period: A blood sample will be collected from the mother within 24 hours after delivery for assessment of serum ocrelizumab concentration. Treatment with commercial ocrelizumab may be resumed at any time after birth for women who decide not to breastfeed. Some women may decide to resume treatment with ocrelizumab whilst breastfeeding. For those women, treatment with ocrelizumab should be restarted after collection of the infant blood sample at Week 6 of life (±7 days) if possible, but the decision is left to the discretion of the woman and the investigator. If the woman switches to another DMT postpartum, the infant blood sample at Week 6 of life (±7 days) will only be collected if the woman is not breastfeeding.

Infant:

At birth, a blood sample will be collected from the umbilical cord (only for live births; no collection should occur in the event of a pregnancy interruption [i.e., therapeutic abortion

or stillbirth]). The target time frame for collection will be within 1 hour after delivery; the actual time of collection after delivery will be recorded. At Week 6 (\pm 7 days) of the infant's life, a blood sample will be collected from the infant (at an on-site visit, or by home nurse visit) for measurement of B-cell levels (the primary endpoint). For preterm infants, blood samples will be collected at the week of life equivalent to term infants (e.g., if birth occurred at gestational Week 35, blood sample would be collected at Week 8 of life).

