4.5.3.2 Laboratory, Biomarker, and Other Biological Samples Umbilical cord blood assessments (target collection time within one hour of birth; only for live births; no collection should occur in the event of a pregnancy interruption [i.e., therapeutic abortion or stillbirth])

• **Ocrelizumab concentration**: a serum sample will be collected for determination of ocrelizumab concentration

Week 6 of Life (±7 days)

- Lymphocyte subtypes: A blood sample will be collected to measure B-cell counts (CD19+), T-cell counts (CD3+, CD4+, CD8+), and NK cell counts (CD16+CD56+).
- **Ocrelizumab concentration:** a serum sample will be collected for determination of ocrelizumab concentration.

Note: If the infant's B-cell levels are below LLN, repeat analyses may be done at unscheduled visits at the discretion of the investigator (in consultation with the Sponsor).

Infant samples will be collected by venipuncture. As per the recommendation of the European Commission ad hoc group (2008) the total blood volume to be collected from an infant in a clinical study should not exceed 0.8–0.9 mL/kg at any time point, or 2.4 mL/kg over any 4-week period throughout the study. If the blood volume collected for an infant (as a result of these limits) is insufficient to carry out all planned assessments, Table 3 shows the order of priority for assessments.

Table 3Prioritization Order for Infant Blood Sample Assessments at
Week 6 of Life (±7 days)

Order of Priority	Assessment		
1	Any safety laboratory samples (scheduled or unscheduled and performed at the discretion of the Investigator)		
2	Lymphocyte subtypes blood sample ^a		
3	Serum ocrelizumab concentration		

NK = natural killer.

^a Blood samples will be collected to measure B-cell counts (CD19+), T-cell counts (CD3+, CD4+, and CD8+), and NK cell counts (CD16+CD56+).

One month (+30 days) after first dose of MMR vaccine (if first dose is administered at 11 months of age or later) OR 1 month (+30 days) after second dose of MMR vaccine (if first dose is administered before 11 months of age) OR at Month 13 of chronological age (+30 days) if MMR vaccine is not planned to be administered

• Lymphocyte subtypes: A blood sample will be collected to measure B-cell counts (CD19+), T-cell counts (CD3+, CD4+, CD8+) and NK cell counts (CD16+CD56+).

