4.1.2 Full Analysis Set (Infants)

The full analysis set of infants (FASI) will include all infants born to women in the FASW who were potentially exposed to ocrelizumab during pregnancy.

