4.4.4 Sensitivity Analysis for Primary Endpoint

The following sensitivity analyses may be performed on the primary endpoint if more than 20% of infants are impacted. Infant with any of the following condition will be considered as being impacted:

- infants blood samples collected outside the Week 6±7 days visit window.
- gestational age is less than 37 weeks, but interval of assessment is not adjusted.
- resume OCR postpartum whilst breastfeeding before sample at Week 6 is taken.

A sensitivity analysis may be conducted substituting any B Cell values with missing data.

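### The Week 6 infant ocrelizumab summary for placental transfer does not separate breastfed infants whose mothers restarted ocrelizumab before the sample

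*SAP*

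**What the plan says.** Protocol Section 2 (Table 1) states the secondary objective as "To evaluate whether there is placental transfer of ocrelizumab from the mother to the infant" and gives it two endpoints: the cord-blood concentration at birth and the infant serum concentration at Week 6. SAP 4.5.2 repeats that purpose for both measurements.

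For the analysis, SAP 4.5.2 says the concentration "in the infant at Week 6 will be presented (including breastfeed prior to sample taken) in the FASI". It adds a listing, an exploratory correlation between maternal and infant concentrations, and the rule that values below the limit of quantification (BLQ) count as zero. SAP 4.1.2 says the FASI "will include all infants born to women in the FASW who were potentially exposed to ocrelizumab during pregnancy".

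On postpartum treatment, Protocol 3.1.3 says "Some women may decide to resume treatment with ocrelizumab whilst breastfeeding". It asks that the restart follow the Week 6 infant sample "if possible, but the decision is left to the discretion of the woman and the investigator". For Week 6, Protocol 4.5.3.2 states that "a serum sample will be collected for determination of ocrelizumab concentration".

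SAP 4.4.4 recognises this situation for the primary B-cell endpoint. One of its three conditions for counting an infant as impacted is "resume OCR postpartum whilst breastfeeding before sample at Week 6 is taken".

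**The concern.** A breastfed infant whose mother had an infusion between delivery and the Week 6 sample has two possible sources of drug: transfer before birth and milk after it. A single serum value cannot tell them apart. If such infants are pooled with the rest, the Week 6 summary no longer answers the question it is assigned.

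The group is small (about 30 infants), and BLQ values are set to zero. A few positive values could therefore determine the mean and suggest persisting placental drug when the source was postnatal.

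**Working it through.** **Who is in the summary.** I set the relevant rules side by side.

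- *Analysis set.* The FASI (SAP 4.1.2) depends only on prenatal exposure. SAP 4.1.6 defines a pharmacokinetic set (PASI) that requires available samples but likewise ignores feeding and maternal restart. SAP 4.5.2 does not use the PASI.
- *Are these infants sampled?* Yes. Protocol 3.1.3 withholds the Week 6 sample only when a breastfeeding woman switches to another disease-modifying therapy. SAP 4.4.1 has a line excluding infants exposed to any such therapy during breastfeeding, but gives resumed ocrelizumab its own line, under which the B-cell data are included.
- *Does a sensitivity analysis cover them?* Not for this endpoint. The SAP 4.4.4 analysis is optional, applies only to the primary endpoint, and needs more than 20% of infants impacted by any listed condition.
- *Is there a split elsewhere?* SAP 4.5.3 splits infant vaccine titers by whether the mother received postpartum ocrelizumab. SAP 4.5.2 has no such split.

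**The plan's own figure.** Evaluable infants (SAP 2.2): 33 × (1 − 0.10) = 29.7, so about 30, as stated. More than 20% of 30 means more than 6, so at least 7 infants.

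**Illustration of size.** The documents give neither the number of affected infants, m, nor their concentration, c. I assume that all other infants are BLQ and counted as zero, and that each affected infant has level c, all of it from milk. Then the mean is m × c / 30.

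| m of 30 | Mean | Median | Above 20% of infants? |
|---|---|---|---|
| 1 | 0.033c | 0 | no |
| 3 | 0.100c | 0 | no |
| 6 | 0.200c | 0 | no |
| 7 | 0.233c | 0 | yes |
| 10 | 0.333c | 0 | yes |

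With these infants shown separately, the mean of the rest is 0 under the same assumption. The median stays at zero up to m = 14, because the 15th and 16th ordered values are then both zero. The last column only shows when this condition alone would reach the SAP 4.4.4 threshold, which does not apply to concentrations in any case.

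The denominator may be below 30. Protocol Table 3 ranks the Week 6 ocrelizumab concentration last of three when blood volume is short, and m/n rises as n falls.

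**The case against.** Several objections have weight.

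- *Milk-derived drug is not shown to be present.* A reader might infer that it is in fact counted as placental transfer. That would need a mother to restart early while breastfeeding, drug to pass into milk, and drug to reach infant serum. The documents quantify none of these steps and advise against the first. Only the conditional statement stands.
- *The bracket in SAP 4.5.2 is loosely worded.* It may mean that feeding status will be displayed. If so, the non-breastfed group would be free of milk exposure, which is some help. The breastfed group would still mix infants of restarting and non-restarting mothers.
- *The correlation may be unaffected.* A reader might infer that these infants also distort it. SAP 4.5.2 does not name the infant or maternal time point, and a correlation of cord with delivery values would not be touched. The point reaches the correlation only if it uses the Week 6 infant value.
- *The effect is on one statistic.* A reader might infer an inflated proportion of infants with detectable drug, but SAP 4.5.2 does not specify that output. SAP Section 4 plans medians and quartiles, and under the assumption above the median stays at zero.
- *The listings would let a careful reader find such infants.* Concentrations and postpartum exposure are both listed. This reduces the harm, but it leaves attribution to cross-reading after the fact, with no planned summary that separates the sources.
- *The endpoint is descriptive and secondary, and cord blood is the more direct measure.* True. This limits the importance of the point without removing it.

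**Conclusion.** The point holds in conditional form. SAP 4.5.2 assigns the Week 6 infant concentration to placental transfer and summarises it in a set that includes, without separation, breastfed infants whose mothers restarted ocrelizumab before the sample. Any milk-derived drug in those infants would be counted in that summary.

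The size is unknown. The figure of m/30 of the affected infants' level rests on three assumptions: 30 infants with a Week 6 concentration, every other infant BLQ, and affected levels due entirely to milk. If no mother restarts before the sample while breastfeeding, the effect is nil.

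Only one of the two endpoints of one secondary objective is involved. The change is still worth making, because the SAP already recognises the condition for B cells and already makes a similar split for titers.

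**What to change.** Amend SAP 4.5.2 as follows.

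- Keep the overall FASI summary of Week 6 concentrations.
- Also present them separately for (a) infants with any breastfeeding before the sample whose mother received ocrelizumab between delivery and the sample, and (b) all other infants. Do the same for any correlation that uses the Week 6 infant value.
- State that the placental-transfer interpretation rests on cord blood and group (b).
- Flag group (a) in the listing.
- Name the time points used in the correlation, and reconcile the set used here with the PASI in SAP 4.1.6.

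The inputs are the recorded infusion and sample dates and the Week 6 feeding data. Feeding status is recorded in categories (Protocol 4.5.3.1), and I found no breastfeeding stop date among the listed items, so whether milk was given after the dose may not always be derivable. Infants of restarting mothers with unclear feeding timing should therefore be placed in group (a).

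The cost is a short SAP amendment, one extra display and slightly fewer infants in the unaffected Week 6 summary. Sampling and treatment do not change.

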4.5.3 Infant Absolute Antibody Immune Response

The infant's antibody (Immunoglobulin [Ig]G) immune response to common childhood immunizations with full or partial doses given prior to 1 year may include (but is not limited to) responses to MMR, diphtheria, tetanus, and pertussis (DTaP), Hemophilus influenzae type b (Hib), hepatitis B virus (HBV) and 13-valent pneumococcal conjugate vaccine (PCV-13), measured 1 month after the first or second dose of MMR vaccine or at Month 13 of age (+30 days) in case MMR vaccine is not planned to be administered.

Summary statistics for each serum IgG antibody titer will be presented in the AIRI and a corresponding listing produced. Results for MMR titers will be summarized together irrespective of whether or not the infant received MMR vaccine. Analysis will be presented for the following subgroups:

- Maternal OCR exposure prior to the study in 3-month interval of before/during pregnancy (3-6 prior LMP, 0-3 month prior to LMP, 1st trimester)
- Type of feed: exclusive breast milk from birth to Month 6 vs others (including complementary feeding [breastmilk + formula milk, in various proportions] and formula feeding [no breast milk])
- Women with/without receiving postpartum ocrelizumab

A listing with all immune responses will be produce.

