Serum concentration of ocrelizumab in the pregnant women/mothers during pregnancy and at delivery, and the serum concentration of ocrelizumab in infants at birth (umbilical cord blood) and at Week 6 of life (or equivalent if preterm birth) will be summarized descriptively.

Mean titers of antibody immune response(s) to vaccinations will be summarized descriptively. The proportion of infants with a positive response (seroprotective titers; as defined for the individual vaccine) to different vaccinations will be calculated and the corresponding two-sided Clopper-Pearson 95% CIs will be presented overall.

Continuous variables at each visit, as well as change from baseline (if applicable) will be analyzed primarily using descriptive statistics. Mean, corresponding 95% CIs, SD, and other statistics will be presented.

Ocrelizumab—F. Hoffmann-La Roche Ltd 63/Protocol MN42988, Version 3

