4. STATISTICAL METHODS

The analysis of this open-label study will be primarily based on descriptive statistical methods. Unless otherwise specified, no statistical tests are planned. Corresponding 95% Cls will be presented as appropriate.

For continuous variables, descriptive statistics (e.g., number of patients [n], mean, standard deviation [SD], median, 25th and 75th percentiles, minimum, maximum) will be calculated and summarized.

For categorical variables, the number and percentage in each category will be displayed.

The analyses outlined in this Statistical Analysis Plan (SAP) supersede those specified in the protocol.

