 - Number of relapses before, during pregnancy (defined by LMP) and after pregnancy (defined as after birth) will be summarized in 3-month interval respectively.
 - Number and percentage of women in each category (0, 1, 2, 3 and ≥4) in
 3-month intervals of before/during/after pregnancy.
 - Number of relapses after first OCR and up to 1 year before pregnancy, during pregnancy, up to 1 year after delivery will be presented. Annualized relapse

rate and 95% CI may also be presented if warranted by the number of data points.

- Mean EDSS score in 3-month interval of before/during/after pregnancy. In case of multiple EDSS score at the same visit, the median will be used.
- Change from baseline in EDSS by visit.
- Presence of any clinically significant abnormalities from the neurological examination (Yes, No) by visit
- Type of neurological abnormality (disability progression independent of relapse, MS relapse, signs or symptoms suggestive of Progressive Multifocal Leukoencephalopathy, Other) by visit

MS relapses, EDSS and neurological examination findings will also be listed. Analysis will also be presented for subgroups based on OCR exposure prior to the study as list in Section 4.5.4.

4.6.5 Women's Neuroaxonal Damage

To detect presence of neuroaxonal damage in the mother during pregnancy and postpartum, serum neurofilament light chain (sNfL) levels are measured at baseline (gestational age Week 24-30), gestational age Week 35, at delivery and postpartum (in line with ocrelizumab administration timepoints). Absolute sNfL levels will be log (base 10) transformed. The geometric mean with corresponding 95% CI and change from baseline will be back transformed and presented. Absolute sNfL levels as well as change from baseline based on log back transformed may also be displayed graphically over time, as appropriate.

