4.8.3.1 General laboratory evaluation

All laboratory assessments in the women (hematology, serum chemistry, urinalysis, HBV serology and serum immunoglobulin concentration) will be summarized in the SAFW or listed when applicable.

Absolute values and change from baseline at each visit will be summarized using standard unit. The baseline value for laboratory assessments summarized in women will be the last value prior to the first dose of study medication. When laboratory data are presented over time, these laboratory values will be time-windowed into a common visit structure. If multiple values of the same laboratory parameter occur within the same time window, the worst value for that parameter will be presented in the summary table.

Unless specified otherwise, any laboratory parameters which are BLQ will be listed, for summaries a value of the LLQ/2 will be imputed. Values above the upper limit of quantification will be summarized at the upper limit of quantification.

For hematology and serum chemistry, the number and percentage of patients with normal/abnormal laboratory outcomes based on normal laboratory ranges will be summarized for each parameter and visit. For urinalysis, the number and percentage with each test result category will be reported for each parameter and visit.

Corresponding patient-level listings will be produced for the following in the SAFW: haematology, serum immunoglobin concentration, laboratory abnormalities for

haematology, laboratory abnormalities for serum chemistry, laboratory abnormalities for uinalysis.

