 To evaluate whether there is placental transfer of ocrelizumab from the mother to the infant 	 Serum concentration of ocrelizumab in the umbilical cord blood at birth (target time frame of blood sampling: within 1 hour after delivery) Serum concentration of ocrelizumab in the infant at Week 6 of life 	
• To evaluate whether infants potentially exposed to ocrelizumab during pregnancy are able to mount humoral immune responses to clinically relevant vaccines	 Mean titers of antibody immune response(s) to common childhood vaccinations with full or partial doses given prior to 1 year, which include responses to diphtheria, tetanus, pertussis, Hib, PCV-13, MMR, and HBV Proportion of infants with positive humoral response (seroprotective titers; as defined for the individual vaccine) to vaccines 	
 To evaluate the levels of ocrelizumab in the mother during pregnancy 	 Serum concentration of ocrelizumab in the mother during pregnancy (time frame of blood sampling: Week 24–30, Week 35) and at delivery (time frame of blood sampling: within 24 hours after delivery) 	
Safety Objectives		
 To evaluate the safety of ocrelizumab in the mother, and the safety of infants potentially exposed to ocrelizumab 	 Rate and nature of adverse events in the mother throughout the study, including changes in clinical and laboratory results Rate and nature of adverse events in the infant throughout the study, including infections and hospitalizations 	
 To evaluate pregnancy and neonatal outcomes 	 Proportion of pregnancies resulting in live births (term and preterm, with and without congenital anomalies), therapeutic abortions, or stillbirths Infant characteristics at birth, including but not limited to body weight, head circumference and length 	
Exploratory Objectives		
• To evaluate the infant's growth velocity and developmental milestones in the first year of life	 Assessment of growth velocity based on age-adjusted body length, weight and head circumference, using growth charts according to the WHO Child Growth Standards, as well as absolute values, at Months 2, 4, 6, 9, and 12 Assessment of child developmental milestones in the domains of communication, gross motor, fine motor, problem solving, and personal-social at Months 2, 4, 6, 9, and 12, using the ASQ-3 	

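### The SAP names no log scale or geometric mean for antibody titres, so by default the mean-titre secondary endpoint becomes a raw-scale mean that responds weakly to a low-responding minority

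*SAP*

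**What the plan says.** The secondary endpoint in both synopses is "Mean titers of antibody immune response(s) to common childhood vaccinations with full or partial doses given prior to 1 year". Protocol 6.4.2 repeats that "Mean titers of antibody immune response(s) to vaccinations will be summarized descriptively", and for continuous secondary variables generally adds "Mean, corresponding 95% CIs, SD, and other statistics will be presented". It names neither the scale nor the CI method.

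SAP 4.5.3 states that "Summary statistics for each serum IgG antibody titer will be presented in the AIRI and a corresponding listing produced". The default in SAP Section 4 is "descriptive statistics (e.g., number of patients [n], mean, standard deviation [SD], median, 25th and 75th percentiles, minimum, maximum", and 95% CIs "will be presented as appropriate". The same section says that the SAP's analyses take precedence over the protocol's. SAP 4.6.3 presents the maternal Week 35 titres in the same way as the infant titres.

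For sNfL, SAP 4.6.5 calls for a log10 transformation, and "The geometric mean with corresponding 95% CI and change from baseline will be back transformed and presented".

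SAP 4.8.3.1 imputes half the lower limit of quantification for values below it, and "Values above the upper limit of quantification will be summarized at the upper limit of quantification". That section opens with the women's laboratory tests. SAP 4.8.3.3, on infant titres, gives no limit rule of its own. SAP 4.5.3 also pools MMR titres whether or not the infant was vaccinated.

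**The concern.** The objective is to learn whether exposed infants can mount vaccine responses. The worrying pattern is a minority who respond poorly. If titres are right-skewed, a raw mean is governed by the highest values and barely moves when a few infants respond badly, while a geometric mean gives a ten-fold deficit its full weight. The SAP's own tetanus and diphtheria cut-offs are a factor of ten apart (0.01 and 0.1 IU/mL in SAP 4.5.3.1), which is how titres are usually read.

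The SAP spells out a log scale where it wants one, for sNfL. A programmer who finds no such instruction for titres would apply the default list to raw values. SAP 4.5.3 also splits the infants into three groups by timing of the last dose, where a single high value carries more weight.

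**Working it through.** **Inputs from the documents.** Expected n: 33 women less 10% gives 33 × 0.9 = 29.7, which reproduces the stated figure of about 30 evaluable infants. The titre set (SAP 4.1.5) may be smaller, because it needs an available titre and a missed Month 13 sample is not a deviation. Neither document states an SD, a precision figure or an assay limit for any titre, so there is no titre figure to reproduce.

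**Assumptions.** Titres are log-normal with log10 SD 0.2 to 0.7. The interval is the ordinary t-interval on raw values. A subgroup of 10 comes from splitting 30 evenly in three. Each simulation setting used 100,000 samples.

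**Step 1: raw mean against geometric mean.** With s = log10 SD × ln 10, the ratio is exp(s²/2). At SD 0.5, s = 0.5 × 2.3026 = 1.151, s²/2 = 0.663 and the ratio is 1.94. Under the same model the arithmetic mean lies at percentile Φ(s/2) = Φ(0.576), about the 72nd, and so is not a typical titre.

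**Step 2: coverage of the nominal 95% interval.**

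| log10 SD | Ratio | Raw mean, n = 30 | Raw mean, n = 10 | Median share of the total from the top infant of 30 |
|---|---|---|---|---|
| 0.2 | 1.11 | 93.8% | 92.5% | 8% |
| 0.3 | 1.27 | 91.9% | 89.6% | 11% |
| 0.5 | 1.94 | 85.8% | 80.5% | 18% |
| 0.7 | 3.67 | 75.9% | 68.6% | 27% |

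The log-scale interval for the geometric mean covered 94.9–95.2% in every setting, as it must when log-normality is assumed. The raw-scale misses are nearly all on one side, with the interval below the true mean. At n = 10 its lower limit is negative, impossible for a titre, in about 1%, 19% and 48% of samples at SD 0.3, 0.5 and 0.7.

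**Step 3: sensitivity to low responders.** Let 6 of 30 infants respond ten-fold lower.
- Expected arithmetic mean: 0.8 + 0.2 × 0.1 = 0.82 of the full-response value, a fall of 18%.
- Geometric mean: 10^(−0.2) = 0.63 of that value, a fall of 37%.

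When such a group is compared with an equal-sized group of full responders at SD 0.5, the affected group still shows the higher arithmetic mean about 30% of the time, against 6% for the geometric mean. At SD 0.3 the figures are 17% and under 1%, and at SD 0.7 they are 37% and 13%.

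**Step 4: effect of capping.** If titres are capped at the 90th percentile (assumed, since no assay limit is given), the t-interval for the capped mean covers about 95%, 94% and 94% at n = 30 for SD 0.3, 0.5 and 0.7, and about 93%, 91% and 89% at n = 10. The capped mean is a different quantity. It lies 9%, 22% and 41% below the uncapped arithmetic mean, while the geometric mean falls by only 3%, 5% and 7%.

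**The case against.** A reader might infer that the SAP prescribes arithmetic means and attaches a faulty interval to them. The documents do not go that far. The word arithmetic appears in neither, the default list is introduced as an example, and SAP 4.5.3 names no CI for titres. An interval comes only from the general wording of Protocol 6.4.2 and the SAP's as-appropriate rule, with no method given. What stands is that nothing directs the analyst to a log scale, and the default leads to raw means.

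A reader might also infer that the interval will certainly under-cover by a wide margin. That depends on an SD and an assay limit that the documents do not give. At SD 0.2 the loss is about one percentage point, and under the assumed cap it nearly disappears at n = 30. This part of the objection stands.

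Third, low responders would not be hidden. The median, quartiles and minimum are in the default list, every response is listed, and SAP 4.5.3.1 reports seroprotection proportions by antigen and subgroup. No test or decision rests on the mean. This also stands and limits the seriousness. It does not justify making the least sensitive summary the headline of a named secondary endpoint.

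Finally, the log scale has a cost of its own. If 20% of values were below the limit (assumed), substituting the limit itself in place of half of it would move the geometric mean by 2^0.2 = 1.15, or 15%. If those values sat 1.5 to 2 log10 units below the responders, the geometric mean would drop to 10^(−0.3) = 0.50 or 10^(−0.4) = 0.40 of the responders' value. This matters most for MMR, where vaccinated and unvaccinated infants are pooled. A log scale alone does not resolve that mixture.

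**Conclusion.** The point holds as a gap in specification that has a clearly better alternative. SAP 4.5.3 and 4.6.3 name no scale for titres, and following the text yields raw-scale means and SDs, while the same SAP uses geometric means for an exploratory marker. Under log-normal titres with log10 SD 0.3 to 0.7, the raw mean is 1.3 to 3.7 times the geometric mean. An uncapped t-interval at n = 30 then covers about 92% falling to 76%. The direction follows from right skew, but the size rests on assumed spreads and on no capping. The weak response of the raw mean to a low-responding minority is the stronger argument, because it does not depend on a CI being reported. The change is worth making before the titre analysis, but the primary endpoint and the seroprotection proportions are unaffected.

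**What to change.** In SAP 4.5.3 and 4.6.3:

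- Report the geometric mean titre with a 95% CI back-transformed from log10 values, alongside the median and range, for each antigen.
- Give the numbers of values below and above the assay limits.
- State explicitly that the half-limit and upper-limit rules of SAP 4.8.3.1 apply to infant and maternal titres, since their present location leaves this unclear.
- Show MMR titres by vaccination status in addition to the pooled summary.
- Keep the seroprotection proportions and the listings. Reverse cumulative distribution plots are optional.

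The cost is SAP wording, one derived variable and a few table rows. No new data are needed. The drawback is that the geometric mean depends on the below-limit substitution, which is why the counts at the limits and the MMR split belong with it.
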